### **Qualitative Interviews:**

Semi-structured qualitative interviews are being conducted with patients, PTs, other health professional primary care team members, medical office assistants, and primary care organizational leaders.

Interviews with patient participants, PTs, and other health professionals have two goals: 1) to explore the experiences and perspectives with the PT-led primary care model for LBP; and 2) to understand how the model of care was implemented, how the intervention interacted with its context, and barriers/facilitators to implementation. Interview guides for interviews with patient participants, PTs, and other health professionals start by exploring experiences with the PT-led primary care model for LBP using open-ended questions and probing. The interview guides then focus on asking participants about how the model of care was implemented, how the intervention interacted with its context, and barriers/facilitators to implementation using questions constructed to align with the CFIR domains. The interview guides for medical office assistants and primary care organizational

leaders will focus on how the model was implemented and contextual factors influencing implementation using the CFIR. Interview guides were pre-piloted with persons with lived experience as patients and primary care team members prior to conducting the interviews.

We are using purposive sampling to recruit 8-12 patient participants with diversity in terms of age, gender, race, household income, LBP-related disability, LBP duration, STarT Back risk categories, and primary care site. We are inviting all PTs who are involved in implementing the PT-led primary care model for LBP to participate in an interview. We are purposively sampling 10-15 primary care health professionals who work with a PT in the PT-led primary care model for LBP, ensuring variation in terms of professional background, gender, and primary care site. We are using purposive sampling to identify four to eight medical office assistants and four to eight primary care organizational leaders who have experienced implementation of the PT-led primary care model. The concept of information power related to our study objectives is being used to determine when to stop interviewing within each informant group based.

Patient participants were asked during their initial consent process for the main trial whether they were willing to be contacted for a follow-up qualitative interview about their experiences with the PT-led model of care. Willing patient participants were contacted within 12 weeks of enrollment. Based on our purposive sampling criteria, research assistants contacted potential participants who had agreed to be contacted to provide additional details about the interview purpose, review the consent process, and arrange a convenient time for the interview. Participants who agreed to take part were then sent a letter of information and consent form in advance. At the time of the interview, the research assistant confirms that the participant has reviewed the consent form, responds to any questions, and obtains verbal consent before proceeding. Recruitment of healthcare providers, medical office assistants, and organizational leaders is being carried out by a study coordinator and research assistant who are familiar with the participating clinical teams. Potential non-patient participants are being invited via email or in-person. Those who indicate interest are scheduled for an interview. As with patient participants, they will receive the letter of information and consent form ahead of the interview, and verbal consent is obtained at the start of the session after confirming their understanding and answering any questions.

### **Protocol and Analysis Plan Amendments:**

Changes to the protocol and analysis plan will be communicated by amending the trial registry at ClinicalTrials.gov and reported in the full trial publication. Investigators and participants will be communicated with as appropriate based on the changes.

### **Analysis**

#### **Effectiveness analysis**

All quantitative analyses will be conducted as per the Intention-To-Treat principle. Descriptive statistics for baseline characteristics and primary and secondary outcomes will be reported by arm using means (SD) or medians (interquartile range) for continuous variables and count (percent) for categorical variables. All analyses will be performed in SAS, version 9.4 (SAS Institute Inc; Cary, NC). Differences between arms will be compared, accounting for site clustering using linear mixed models and generalized estimating equations (GEE), and significance will be reported with p-values.

#### **Patient health and experience outcomes**

For our patient health outcomes, we will use linear mixed models to estimate individual patient participant outcomes adjusting for clustering by primary care centre. Our primary outcome (RMDQ) with repeated measures at baseline and the 6-week, 3-, 6-, 9-, and 12-month follow-up time points will be analyzed using linear mixed regression (using *PROC MIXED* in SAS), estimated using restricted

maximum likelihood (REML) estimation and a Kenward-Rogers degrees of freedom correction to account for a small number of clusters. The model will include fixed effects for time, intervention group by time interaction, (omitting the group main effect to ensure baseline differences are constrained to zero), factors used in the covariate-constrained allocation procedure (rurality of the cluster, number of active patients) and other pre-specified covariates associated with LBP-related disability (patient participant age, sex, income, highest level of education achieved, duration of current episode of LBP, Functional Comorbidity Index score). The correlation in repeated measures on the same participant will be modeled using a suitable covariance structure, identified using information criteria (AIC/BIC). To account for clustering within practices, site will be modeled as a random effect. The intervention effect will be obtained as the adjusted least square mean difference between arms at 12 months, with 95% confidence intervals. Secondary comparisons will be obtained using least square mean differences at intermediate time points.

The use of REML estimation under an assumption of Missing At Random (MAR) allows the use of all available data without the need for multiple imputation. To examine the risk of bias due to missing data, we will compare the characteristics of those remaining and those lost to follow-up to identify factors associated with attrition. We will perform a sensitivity analysis for a missing not at random (MNAR) departure from our MAR assumption using a delta-adjusted imputation pattern mixture model approach to investigate the robustness of our trial outcomes with regard to the missing values of the RMDQ. Within this sensitivity analysis approach, we will start with the posterior distributions suggested by an imputation model using multiple imputation by chained equation. Our imputation model will incorporate all variables in our primary analysis model, along with the last-observed-before-time covariates, and additional covariates needed for the pattern mixture. The sensitivity parameter (delta) will be introduced to explore how a departure from MAR affects results by specifying a maximum delta for each pattern of missing. We will set the maximum delta to be twice the residual sample standard deviation from the observed data fit of the primary linear mixed model. Our sensitivity analysis will use multiple imputation 9 times to generate estimated treatment effects for a range of sensitivity.

Pain intensity, health-related quality of life (EQ-5D-5L), PSEQ, PCS, TSK-11, and PHQ-2 outcomes will be analyzed as described for the primary outcome, adjusted for the same covariates. Patient satisfaction and global rating of change outcomes have no baseline measures, and will be analyzed using ordinal logistic regression with clusters as random effects, adjusting for the same covariates as described above. When individual items are missing from within any of the questionnaires, we will use simple mean imputation as suggested by Chavance. Serious adverse events will be presented descriptively by arm due to low expected counts. Any adverse events (yes/no) will be presented as incidence rates with confidence intervals and compared by calculating relative risks with confidence intervals from robust Poisson regression using GEE-type robust variance estimators (using *PROC GLIMMIX* with *EMPIRICAL* option in SAS) to account for clustering and using an exchangeable working correlation matrix. We will use empirical covariance (“sandwich”) bias-adjusted (residual-based) estimators and the Fay and Graubard correction to account for small number of clusters in all models comparing incidence rates. In the case of non-convergence or unstable estimates due to the small number of clusters, we would attempt to fit the model using an independent working correlation matrix. Other information related to non-serious adverse events (i.e., severity and duration) will be reported descriptively.

We have planned a secondary analysis, a responder analysis, to compare the proportion of participants who experience a meaningful improvement in disability (RMDQ) in the PT-led primary care model arm versus the usual care arm. We will define a meaningful improvement as an improvement of greater than or equal to 30% improvement on the RMDQ, corresponding to an established minimally important difference among people with LBP. We will calculate the proportion of participants who

experience a meaningful improvement in each arm and compare between groups using robust Poisson regression, with GEE-type robust variance estimators to account for clustering. We will use empirical covariance (“sandwich”) bias-adjusted (residual-based) estimators and the Fay and Graubard correction to account for small number of clusters.

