### **Sample Size and Power Calculations:**

We used the methodology of Teerenstra et al. to calculate the required number of clusters based on an ANCOVA analysis for the primary outcome (Roland-Morris Disability Questionnaire [RMDQ]) at 12 months adjusting for baseline. Our target sample was 20 clusters (10 per arm) allowing for 1560 patient participants (78 per practice before attrition). Conservatively accounting for attrition of two clusters (resulting in 18 clusters) and 20% of patients (resulting in 63 patients/cluster), this target would achieve 90% power to detect a minimally important mean difference of 2.5 points (Cohen's  $d=0.4$ ) using a two-sided  $\alpha=0.05$  and assuming a standard deviation (SD) of 5.7 points based on pilot study data, a conservative intracluster correlation coefficient of 0.1, a cluster autocorrelation coefficient (correlation between cluster means at baseline and follow-up) of 0.5, and an individual autocorrelation coefficient (correlation between participant scores at baseline and follow-up) of 0.6 informed by our pilot study. An average rate of 1.5 patient participants per site each week over one year would achieve the recruitment target of 1560 participants, which we anticipated based on our pilot study where we recruited and retained four sites and achieved a recruitment rate of >1.7 participants/site/week. Recruitment of 400 patient participants across 18 clusters (22 participants/cluster) would achieve 80% power.

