### Subgroup analyses

In alignment with sex and gender equity in research (SAGER) guidelines, we plan to conduct exploratory analyses for each of our effectiveness outcomes for males and females to explore potential sex differences in each of these outcomes. We will include sex and its interaction with time and group by time in the models. We will report the interaction p-value along with forest plots to visualize the subgroup treatment effects, along with 95% confidence intervals.

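### Dropping the group main effect does not by itself force a zero baseline difference in the primary model; the coding that would do so is not stated

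*Combined protocol and SAP*

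**What the plan says.** The Analysis part of the combined protocol and SAP, under Patient health and experience outcomes, puts RMDQ at baseline and at five follow-ups into one outcome vector, "analyzed using linear mixed regression (using *PROC MIXED* in SAS". The mean model has "fixed effects for time, intervention group by time interaction, (omitting the group main effect to ensure baseline differences are constrained to zero". The remaining fixed effects are two cluster factors (rurality, practice size) and six patient covariates (age, sex, income, education, episode duration, comorbidity index). Baseline RMDQ is not among them. The treatment effect is the least-squares mean difference at 12 months, with the earlier visits as secondary comparisons. The plan gives no CLASS statement, code or coding of the arm variable.

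Sample Size and Power Calculations says the trial team used a published method to "calculate the required number of clusters based on an ANCOVA analysis for the primary outcome", with adjustment for baseline. For a "minimally important mean difference of 2.5 points" it states that "this target would achieve 90% power".

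The same model is carried over to pain, EQ-5D-5L, PSEQ, PCS, TSK-11 and PHQ-2: these "outcomes will be analyzed as described for the primary outcome, adjusted for the same covariates". Under Subgroup analyses the sex model extends it: "We will include sex and its interaction with time and group by time in the models".

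**The concern.** The plan gives a mechanism (omit the main effect) and a result (zero baseline difference). Under the usual coding in the named procedure, the first does not produce the second. When visit is a six-level factor, an arm-by-visit interaction without the arm main effect has one arm contrast for every visit, baseline included. A programmer who follows the sentence literally gets a model that runs without warning and leaves the baseline difference free.

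This matters because the constraint is the only route by which baseline RMDQ enters the treatment comparison. Without it, and with complete data, the 12-month contrast is a comparison of follow-up means, adjusted only for the other covariates. The precision that the sample size section counts on is not delivered. The wording also admits two different primary estimates, depending on a coding choice that the plan does not record.

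**Working it through.** **1. What the fixed effects span.** Two arms by six visits gives 12 cell means. The rank of the design matrix is the number of means left free.

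| Mean model | Rank |
|---|---|
| visit + arm + arm-by-visit, CLASS coding | 12 |
| visit + arm-by-visit, no arm main effect, CLASS coding | 12 |
| the two matrices above, side by side | 12 |
| visit + arm-by-visit, arm set to reference on baseline records | 11 |
| five follow-up indicators + arm times those indicators | 11 |

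The first two models span the same space, so omitting the main effect changes the labels of the parameters and not the fit. Entering arm as a 0/1 number with visit as CLASS also gives 12. A shared baseline mean needs 11. In the sex model, full CLASS coding leaves all 24 arm-by-visit-by-sex means free, against 22 when the arms share a baseline mean within each sex.

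**2. Inputs**, all from Sample Size and Power Calculations: difference 2.5, SD 5.7, two-sided alpha 0.05, ICC 0.1, cluster autocorrelation (CAC) 0.5, individual autocorrelation (IAC) 0.6, and 18 clusters (k = 9 per arm) of m = 63, or of m = 22 in the smaller scenario.

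**3. Formulas.**
- DE = 1 + (m − 1) × ICC
- r = (m × ICC / DE) × CAC + ((1 − ICC) / DE) × IAC
- Var(adjusted) = 2 × SD² × DE × (1 − r²) / (k × m)
- Var(unadjusted): the same with r = 0
- Power (normal) = Φ(2.5 / SE − 1.96)

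**4. Reproducing the plan, m = 63.** DE = 1 + 62 × 0.1 = 7.2. r = 0.875 × 0.5 + 0.125 × 0.6 = 0.5125. Var = 2 × 32.49 × 7.2 × (1 − 0.2627) / 567 = 0.608, so SE = 0.780. Power = Φ(3.205 − 1.960) = 89.3%, which agrees with the stated 90%.

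**5. Literal CLASS coding, m = 63.** Var = 2 × 32.49 × 7.2 / 567 = 0.825, so SE = 0.908. Power = Φ(2.752 − 1.960) = 78.6%. The variance is 1 / 0.7373 = 1.36 times larger and the SE 16% larger.

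**6. m = 22.** DE = 3.1 and r = 0.529. SE is 0.856 constrained and 1.009 unconstrained.

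| Scenario | SE, shared baseline | SE, free baseline | Power, normal | Power, t on 16 df |
|---|---|---|---|---|
| 18 × 63 | 0.780 | 0.908 | 89.3% → 78.6% | 85.3% → 73.4% |
| 18 × 22 | 0.856 | 1.009 | 83.2% → 69.8% | 78.3% → 64.4% |

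**7. Checks.** Generalised least squares over all six visits, using these correlations, gave the same standard errors. In 20,000 simulated trials (baseline and 12 months, 18 × 63) power was 89.4% constrained and 78.6% unconstrained. The unconstrained estimate equalled the raw 12-month difference to rounding error. At m = 63, reaching 90% on the normal basis takes 10 clusters per arm with the constraint and 13 without.

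**8. Baseline imbalance.** At 18 × 63 the constrained model corrects the 12-month estimate by 0.51 points per 1-point baseline difference; the unconstrained model corrects by 0. The chance baseline difference has an SD of about 0.91, so the uncorrected part has an SD of about 0.51 × 0.91 = 0.46 points.

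**The case against.** The strongest reply is that the plan does prespecify the property that matters. It says the baseline difference is to be zero, cites a methods paper for it and gives no code, so a program with a free baseline difference would depart from its stated purpose. Under five follow-up indicators with baseline as reference, the group main effect is exactly the baseline difference, and omitting it does what the sentence says while each visit effect stays free. Setting arm to the reference level at baseline works too and keeps the same list of fixed effects. All of this stands. It means that failure depends on coding the documents do not give. It does not rescue the wording, because the only mechanism named is the omission, and under standard CLASS coding that omission has no effect.

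The size can also be challenged. The inputs are cautious: with all 20 sites retained and 62.4 patients each, power is 92.2% against 82.6%. With an ICC of 0.05, as an assumption, it is 99.0% against 95.4% at 18 × 63. The gap also depends on the CAC: at 0 the constraint gains almost nothing (78.8% against 78.6%), and at 0.8 it gains more (99.2% against 78.6%). The eight listed covariates may recover part of the loss; the documents do not say how much.

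A reader might infer that the planned power is lost, that baseline is never used, that the estimate is biased, or that only continuous time could impose the constraint. The documents support none of these. Power is reduced. With missing follow-up, likelihood estimation still borrows from baseline within arm. The randomised contrast stays unbiased, and the plan describes steps against recruitment bias. Categorical time with suitable coding imposes the constraint.

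**Conclusion.** The rule is wrong as written. Under the CLASS coding that PROC MIXED and visit-specific least-squares means imply, omitting the group main effect does not impose the constraint the plan claims for it, and no other term adjusts for baseline RMDQ. The documents do not show that the analysis will be coded this way, only that the sentence, followed literally, leads there.

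If it is, the cost on the plan's inputs is about 11 percentage points of power at 18 × 63 and about 13 at 18 × 22, together with uncorrected chance imbalance at baseline. These figures assume complete data, the correlations in the sample size section and no gain from other covariates. The secondary outcomes and the exploratory sex model inherit the same ambiguity; they are not separate evidence for it.

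**What to change.** Replace the parenthesis on omitting the group main effect with:

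> Fixed effects for visit (six levels) and arm-by-visit terms for the five follow-up visits only; arm is set to the reference level on baseline records so that both arms share one baseline mean (11 arm-by-visit mean parameters).

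The count of 11 rather than 12 gives the programmer a direct check on the fitted model. Least-squares mean differences at every follow-up visit remain available. Apply the same coding to the secondary outcomes that follow the primary model. In the sex model, allow arm terms, overall and by sex, at follow-up visits only (22 means, not 24).

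The cost is one sentence in the plan and one derived variable in the program. Trial Status says analysis starts only after data collection ends, and the amendments section provides the route through the trial registry, so the change can be made before any outcome is analysed.

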### **Allocation of Participating Primary Care Teams to Trial Groups:**

Restricted randomization is recommended for cluster randomized trials to ensure the arms are balanced at baseline. We used covariate-constrained randomization with 1:1 ratio to the intervention and comparison arms to retain the merits of random allocation while ensuring baseline balance across the arms. We stratified by location (Southeastern Ontario or Interior British Columbia) and included the following covariates: number of active patients and rural vs. urban setting. Our maximum tolerable difference in the rurality indicator was 1 and the strata balancing criteria for number of active patients was set to 10%. An independent statistician implemented the procedure using a SAS macro. Concealment was maintained by ensuring each practice had an anonymized code and performing randomization after all sites were recruited.

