### **Recruitment:**

We recruited 20 sites (14 in Ontario and 6 in British Columbia, Canada). Site recruitment focused primarily on the engagement of contacted sites to reduce the risk of site withdrawl. For patient participant recruitment, staff at each primary care site screened patients for their willingness to participate when they called to book an appointment. If patients booked online, their reason for visit was screened by the clinic staff and staff reached out to potential participants for their willingness to be contacted by a research assistant. Trained research assistants screened potential participants using inclusion/exclusion criteria and enrolled consenting patients. Patients who raised LBP with any provider during a clinical encounter were also identified as potential participants. In these cases, they were directed to the administrative team, who then connected them with a research assistant for screening and enrollment. Balance in recruitment across arms and across clusters was monitored throughout the study and strategies were implemented to maintain consistent implementation of recruitment processes across sites.

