## **2. Comparison: Usual Physician-Led Care**

The usual physician- or nurse practitioner-led primary care intervention has been unstandardized to reflect usual primary care clinical practice in Canada. Our pilot study suggested the most common management approaches in the usual care model included: diagnostic imaging (12% of patients), medication renewal (21%), new medication prescription (14%), notes to employers (12%), and referral (PT 23%, chronic pain clinic 5%, massage therapy 5%, physician specialists 5%, and dietician 2%). Interventions provided or recommended by the physician have been and will continue to be recorded and monitored throughout the full trial.

There are no required or prohibited concomitant treatment options for either treatment arm. Should a participant choose to explore other or additional treatment options within their primary care team or from other health service providers, they are free to do so. This was made clear in the letter of information and consent form provided to the participants upon entry to the study.

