### **Frequency and Duration of Follow-Up:**

Patient characteristics and demographic information were collected at baseline. All patient-reported outcome measures are being collected at baseline, 6 weeks, and 3, 6, 9, and 12 months from the initial visit, with the primary comparison at 12 months. Patient satisfaction, global rating of change, adverse effects, and healthcare utilization are being collected at follow-up time points only. Patient adherence to PT recommendations is being collected at the 6-week follow-up.

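### Allocation was stratified by location, but no analysis model includes location: no bias is expected, yet standard errors can be too large for outcomes without a baseline.

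*Combined protocol and SAP*

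**What the plan says.** The section on allocation of primary care teams states: "We stratified by location (Southeastern Ontario or Interior British Columbia) and included the following covariates: number of active patients and rural vs. urban setting". The Recruitment section gives the stratum sizes: "We recruited 20 sites (14 in Ontario and 6 in British Columbia, Canada".

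Under Analysis, Patient health and experience outcomes, the RMDQ model sets out to adjust for the factors used in the allocation procedure, but names only "rurality of the cluster, number of active patients) and other pre-specified covariates associated with LBP-related disability". Clustering is handled by one statement: "site will be modeled as a random effect".

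The same list is then reused:
- for the other patient-reported outcomes, including satisfaction and global rating of change;
- for healthcare utilization and missed activities, where the two cluster-level covariates are written out again without location;
- in the Economic evaluation;
- in the between-arm comparisons of the Process evaluation analysis.

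The adverse-event and responder models state no covariates and are outside this point. The Economic evaluation does expect differences between jurisdictions, but handles them with a random site effect.

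**The concern.** A stratifier that predicts the outcome belongs in the analysis. Stratified 1:1 allocation of 14 and 6 sites implies about 7:7 and 3:3 by arm (inferred; the split is not printed). A regional difference in level therefore cancels out of the arm contrast. A model without a location term still leaves that difference in the between-site variance, and a random site effect does not remove it. The reported SE then exceeds the true one, intervals are too wide and tests reject too rarely, to the extent that rurality and practice size do not already explain the difference.

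The effect should be largest where no baseline value can absorb the regional difference. The follow-up section says "Patient satisfaction, global rating of change, adverse effects, and healthcare utilization are being collected at follow-up time points only". Costs are also built from follow-up data. These outcomes carry most of the second research question.

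**Working it through.** **Inputs.** From Sample Size and Power Calculations: SD 5.7, difference 2.5, ICC 0.1, cluster autocorrelation 0.5, individual autocorrelation 0.6, 18 clusters of 63, and the smaller scenario, "Recruitment of 400 patient participants across 18 clusters (22 participants/cluster) would achieve 80% power". From Recruitment: 14 and 6 sites. The Ontario–BC gap d (in SD units) is not in the documents and is assumed throughout. ICC 0.1 is the plan's RMDQ value and is borrowed for the other outcomes.

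**1. The plan's own power figure.**
- Variance of a site mean: v = 5.7² × (0.1 + 0.9/63) = 3.713.
- Baseline–follow-up covariance: c = 5.7² × (0.05 + 0.54/63) = 1.903.
- SE = √(2(v − c²/v)/9) = 0.780.
- Power = Φ(2.5/0.780 − 1.96) = 89.3%, matching the stated 90%.
- With a t distribution, power is 85.3% on 16 df, 84.6% on 14 df (rurality and size fitted) and 84.2% on 13 df (location added).

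**2. Outcomes without a baseline (linear-scale approximation).**
- Site-mean variance in SD units: V = 0.1 + 0.9/63 = 0.1143.
- Variance due to region: g = 0.7 × 0.3 × d² = 0.21d².
- Gap on top of the ICC: SE ratio = √((V + g)/V). Example, d = 0.2: g = 0.0084, √(0.1227/0.1143) = 1.036.
- Gap counted inside the ICC: SE ratio = √(V/(V − g)).
- The effect is set to give 80% power with no gap and no location term (20 sites, 16 df). Leaving location out multiplies the critical value by the SE ratio. Including it uses 15 df.

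| Gap (SD) | 0.1 | 0.2 | 0.3 | 0.4 |
|---|---|---|---|---|
| On top: SE overstated | 0.9% | 3.6% | 8.0% | 13.8% |
| On top: actual alpha | 4.8% | 4.3% | 3.6% | 2.8% |
| On top: power without location | 79.5% | 77.9% | 75.2% | 71.3% |
| On top: power with location | 79.7% | 79.7% | 79.7% | 79.7% |
| Inside: SE overstated | 0.9% | 3.9% | 9.5% | 19.0% |
| Inside: power without location | 80.2% | 80.8% | 81.9% | 83.6% |
| Inside: power with location | 80.4% | 82.6% | 86.3% | 91.3% |

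Variations, gap on top:
- 22 per site (V = 0.1409): SE +0.7 / 2.9 / 6.5 / 11.3%; power without location 79.6 / 78.3 / 76.1 / 73.0%.
- Half the regional variance absorbed by rurality and size: SE +0.5 / 1.8 / 4.1 / 7.1%; power 79.7 / 78.9 / 77.6 / 75.7%.

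A separate simulation (20,000 trials per setting, 63 per site) let location carry 10, 25 or 50% of the between-site variance, equal to gaps of 0.22, 0.35 and 0.49 SD. The closed-form SE ratios are 1.05, 1.13 and 1.33. Simulated type I error without location was 4.2, 2.6 and 0.8%, about 5% with it, and bias was about zero.

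For scale, the pilot's usual-care figure is "diagnostic imaging (12% of patients" in the documents. The SD is √(0.12 × 0.88) = 0.325, so 0.1 / 0.2 / 0.4 SD is 3.2 / 6.5 / 13.0 percentage points.

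**3. RMDQ.** The planned repeated-measures model was simulated with a site random intercept (REML, 20 sites, 63 per site, six time points).
- Constant 2-point gap: mean 12-month SE 0.2843 without location, 0.2824 with it, a 0.7% difference.
- Gap reaching 2 points only by 12 months: a location main effect changes the SE by 0.0–0.2%, location-by-time by 0.9–2.2%.

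A cluster-mean ANCOVA, which the plan does not specify, gives somewhat more. With 18 sites and a constant gap of 1.2 / 2.0 / 2.5 points on top of the ICC, the reported SE exceeds the true SE by 1.2 / 2.3 / 3.0%. Power is 83.9 / 83.0 / 82.3% without location, against 84.2% with it.

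**The case against.** The omission itself is not disputable. The case against concerns its weight.

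- **The primary model hardly changes.** This stands for a site random intercept. It is conditional, however: if a site-by-time random effect were added, the RMDQ SE without location would be about 5% larger than with it (location carrying 25% of between-site variance) to 15% larger (50%). The simulated intercept-only SEs (about 0.28) also lie far below the empirical SD (about 0.83). That is a separate problem, and it limits what the RMDQ percentages can show.
- **The fall in power depends on adding the gap to an ICC the plan already calls conservative** ("a conservative intracluster correlation coefficient of 0.1"). At 0.4 SD the total ICC becomes (0.1 + 0.0336)/1.0336 = 0.129. This is fair. With the gap inside ICC 0.1, power without location stays above 80%, and the loss is power forgone (83.6 against 91.3% at 0.4 SD). Either way, including location is better at 0.2 SD and above.
- **The top of the range is large.** On the imaging rate, 0.4 SD means about 8% against 21% between regions. This stands; the lower half of the range is more plausible, and at about 0.1 SD nothing is gained.
- **Costs are a weaker example than utilization.** Public services and drugs are priced from Ontario schedules in both provinces, so only resource quantities, self-reported expenses and wages can differ by region. This narrows the point for costs but does not remove it.
- **More terms strain rare-event models.** True with six BC sites, and the remedy has to provide for it.

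**Conclusion.** The concern holds. Location was the stratifier, no model includes it, and no reason is given. No bias and no inflated type I error follow; the consequence is lost precision. For outcomes without a baseline, the SE is overstated by 3.6 to 13.8% at assumed gaps of 0.2 to 0.4 SD on top of ICC 0.1, roughly half that if rurality and practice size absorb half the regional variance, and by a negligible amount at 0.1 SD or below. For the RMDQ the effect is small under a site random intercept.

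These sizes rest on an assumed gap, a 7:7 and 3:3 split, a borrowed ICC and a linear approximation for count, binary and ordinal outcomes. Confidence in the size is therefore moderate. The change is worth making because the trade is asymmetric: a fraction of a point of power if region is irrelevant, against about 2 to 8 points if the gap is 0.2 to 0.4 SD on top of the ICC.

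**What to change.** Before analysis starts:
- Add location as a fixed effect to the primary model and to every model that uses the shared covariate list.
- State where location sits in the covariate-removal order that the utilization section sets for non-convergence, since BC has only six sites.
- Treat location-by-time as optional in the repeated-measures models, useful only if the regions are expected to diverge during follow-up.
- If location is omitted on purpose, give the reason.

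The cost is SAP wording and an amendment to the registry, the route the plan already sets out. Statistically it is one cluster-level degree of freedom: if region explains nothing, 80.0% power becomes 79.7% (20 sites) or 79.5% (18 sites), and RMDQ power goes from 84.6 to 84.2%. Location-by-time would add five more fixed effects. In the ordinal logistic models the odds ratio becomes conditional on location as well, a slight change of estimand that should be noted when reporting.
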